4.2 Inclusion Criteria

Each subject must meet the following criteria to be enrolled in this study:

1. Be at least 18 years of age.
2. Have stage 3 or 4 CKD (eGFR of ≥ 15 to <60 mL/min/1.73m² using the Modification of Diet in Renal Disease equation).
3. Be without any disease state or physical condition that might impair evaluation of safety and efficacy or which, in the Investigator's opinion, would interfere with study participation, including:
 - a. Serum albumin ≤ 3.0 g/dL;
 - b. Serum transaminase (alanine transaminase, glutamic pyruvic transaminase, aspartate aminotransferase or glutamic oxaloacetic transaminase) > 2.5 times the upper limit of normal at screening; and,
 - c. Urinary albumin excretion >3000 μ g/mg creatinine.
4. Exhibit during the initial Screening Visit:
 - a. Plasma iPTH ≥ 65 pg/mL and <400 pg/mL if receiving calcitriol or other 1 α -hydroxylated vitamin D analog (paricalcitol or doxercalciferol); or
 - b. Plasma iPTH ≥ 85 pg/mL and <500 pg/mL if not receiving calcitriol or other 1 α -hydroxylated vitamin D analog;
 - c. Serum total 25-hydroxyvitamin D <30 ng/mL, unless taking vitamin D supplementation (including multivitamins and fish oil); and,
 - d. If taking calcitriol or another 1 α -hydroxylated vitamin D analog, subjects must forgo treatment with these non-study agents for the duration of the study and undergo a 4-week washout period and meet inclusion criterion 5.
 - e. For subjects who are taking vitamin D supplementation (including multivitamins or fish oil), they must forgo treatment with these non-study agents for the duration of the study. If the serum 25-hydroxyvitamin D level is <30 ng/mL, there is no need for the subjects to complete a washout period as a result of vitamin D supplementation. If, however, serum 25-hydroxyvitamin D level is ≥ 30 ng/mL, the subjects must undergo a 4-week washout period and meet inclusion criterion 5. If at the end of 4 weeks of washout, the 25 hydroxyvitamin D level is still ≥ 30 ng/mL, the washout may be extended by up to another four weeks for a total of 8 weeks.
5. Exhibit after the washout period (if required):
 - a. Plasma iPTH ≥ 85 pg/mL and <500 pg/mL;

- b. Corrected serum calcium <9.8 mg/dL; (corrected for serum albumin)
- c. Serum total 25-hydroxyvitamin D <30 ng/mL; and,
- d. Serum phosphorus <5.5 mg/dL.
6. If taking more than 1,500 mg/day of elemental calcium, reduce calcium use (to approximately 1,000 to \leq 1,500 mg/day) for the duration of the study.

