4.3 Exclusion Criteria

Subjects who meet any of the following criteria will be excluded from the study:

1. History of or planned kidney transplant or parathyroidectomy.
2. History (prior 3 months) of corrected serum calcium \geq 9.8 mg/dL or serum phosphorus \geq 5.5 mg/dL if not receiving calcitriol or other 1 α -hydroxylated vitamin D analog.
3. Need for phosphate binders to maintain the serum phosphate < 5.5 mg/dL or use of phosphate binders within 4 weeks prior to screening.
4. Use of calcimimetic therapy (cinacalcet or etelcalcetide) within 12 weeks of screening.
5. Receipt of bisphosphonate therapy or other bone modifying treatment within 6 months prior to enrollment.
6. Known previous or concomitant serious illness or medical condition, such as malignancy, human immunodeficiency virus, significant gastrointestinal or hepatic disease, intestinal malabsorption disorder, hepatitis or cardiovascular event that in the opinion of the Investigator may worsen or reduce life expectancy, and/or interfere with participation in the study.
7. History of neurological/psychiatric disorder, including psychotic disorder or dementia, or any reason which, in the opinion of the Investigator makes adherence to a treatment or follow-up schedule unlikely.
8. Known or suspected hypersensitivity to any of the constituents of the study drugs.
9. Currently participating in, or has participated in, an interventional/investigational study within 30 days prior to study screening.

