4.3 Contraindications

- Hypersensitivity to the active substance or to any of the excipients included in [section 6.1](#).
- Hypercalcaemia (calcaemia > 10.5 mg/dL), hypercalciuria (abnormally high excretion of calcium in the urine).
- Calcium lithiasis.
- Hypervitaminosis D.

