4.4 Special warnings and precautions for use

- The serum levels of 25-OH-cholecalciferol reflect the patient's vitamin D status, but in order to obtain an adequate clinical response to the oral administration of calcifediol, there must also be adequate calcium intake in the diet. Therefore, to control the therapeutic effects, in addition to the 25-OH-cholecalciferol, the calcium, phosphorous, alkaline phosphatase, and urinary calcium and phosphorous in the serum must be monitored over 24 hours; a drop in the

serum levels of alkaline phosphatase normally precedes the appearance of hypercalcaemia. Once these parameters are normal in the patient and the patient is on a maintenance treatment regimen, the above-mentioned measurements must be taken, in particular the serum levels of 25-OH-calciferol and calcium.

- **Hepatic or gallbladder insufficiency:** In the event of hepatic insufficiency, an inability to absorb calcifediol may occur through bile salts not being produced.
- **Renal insufficiency:** Administration with caution is advised. The use of this medicinal product in patients with chronic kidney disease must be accompanied by regular checks of plasma calcium and phosphorous, and to prevent hypercalcaemia. As the kidneys will give rise to calcitriol, in the event of severe renal insufficiency (renal creatinine clearance less than 30 mL/minute) a very significant decrease in the pharmacological effects may occur.
- **Cardiac insufficiency:** Particular caution is required. The individual's calcium level must be monitored at all times, particularly in patients undergoing treatment with digitalis medication, as it may cause hypercalcaemia and the appearance of arrhythmia; it is advised to perform these measurements twice a week at the start of treatment.
- **Hypoparathyroidism:** 1-alpha-hydroxylase shall be activated by the **CCI** [REDACTED], therefore in the event of parathyroid insufficiency, the calcifediol activity may decrease.
- **Renal calculi:** The calcium level must be controlled as vitamin D, by increasing calcium absorption, may aggravate the symptoms. Vitamin D levels must only be administered in these patients if the benefits outweigh the risks.
- In patients with long-term immobilisation, dose reduction may be necessary on occasion to avoid hypercalcaemia.
- There are diseases that affect the intestine's capacity to absorb vitamin D, as in the case of malabsorption syndrome or Crohn's disease.

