4.3 Contraindications

- Hypersensitivity to the active substance(s) or to any of the excipients.
- Hypercalcaemia and/or hypercalciuria.
- Nephrolithiasis and/or nephrocalcinosis
- Serious renal impairment
- Hypervitaminosis D
- Pseudohypoparathyroidism as the vitamin D requirement may be reduced due to phases of normal vitamin D sensitivity, involving the risk of prolonged overdose. Better-regulatable vitamin D derivatives are available for this.
- Pregnancy
- Children and adolescents (under 18 years of age)

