4.4 Special warnings and precautions for use

Vitamin D3 should be used with caution in patients with impairment of renal function and the effect on calcium and phosphate levels should be monitored. The risk of soft tissue calcification should be taken into account.

Caution is required in patients receiving treatment for cardiovascular disease (see [section 4.5](#) Interaction with other medicinal products and other forms of interaction - cardiac glycosides including digitalis).

InVita D3 should be prescribed with caution in patients with sarcoidosis, due to a possible increase in the metabolism of Vitamin D3 in its active form. In these patients the serum and urinary calcium levels should be monitored.

Allowances should be made for the total dose of Vitamin D3 in cases associated with treatments already containing Vitamin D3, foods enriched with Vitamin D3, cases using milk enriched with Vitamin D3, and the patient's level of sun exposure.

There is no clear evidence for causation between Vitamin D3 supplementation and renal stones, but the risk is plausible, especially in the context of concomitant calcium supplementation. The

need for additional calcium supplementation should be considered for individual patients. Calcium supplements should be given under close medical supervision.

Oral administration of high-dose Vitamin D3 (500,000 IU by single annual bolus) was reported to result in an increased risk of fractures in elderly subjects, with the greatest increase occurring during the first 3 months after dosing.

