4.9 Overdose

Symptoms of overdose

Ergocalciferol (vitamin D2) and colecalciferol (vitamin D3) have a relatively low therapeutic index. The threshold for vitamin D intoxication is between 40,000 and 100,000 IU daily for 1 to 2 months in adults with normal parathyroid function. Infants and small children may react sensitively to far lower concentrations. Therefore, it is warned against intake of vitamin D without medical supervision.

Overdose leads to increased serum and urinary phosphorus levels, as well as hypercalcaemic syndrome and consequently calcium deposits in the tissues and above all in the kidneys (nephrolithiasis, nephrocalcinosis) and the vessels.

Discontinue InVita D3 when calcaemia exceeds 10.6 mg/dl (2.65 mmol/l) or if the calciuria exceeds 300 mg/24 hours in adults or 4-6 mg/kg/day in children.

Chronic overdosage may lead to vascular and organ calcification, as a result of hypercalcaemia. The symptoms of intoxication are little characteristic and manifest as nausea, vomiting, initially also diarrhoea, later constipation, loss of appetite, weariness, headache, muscle pain, joint pain, muscle weakness, persistent sleepiness, azotaemia, polydipsia and polyuria and, in the final stage, dehydration. Typical biochemical findings include hypercalcaemia, hypercalciuria, as well as increased serum 25 hydroxy colecalciferol concentrations.

Treatment of overdose

Symptoms of chronic vitamin D overdosage may require forced diuresis as well as administration of glucocorticoids or calcitonin.

Overdosage requires measures for treating the - often persisting and under certain circumstances life- threatening - hypercalcaemia.

The first measure is to discontinue the vitamin D preparation; it takes several weeks to normalise hypercalcaemia caused by vitamin D intoxication.

Depending on the degree of hypercalcaemia, measures include a diet that is low in calcium or free of calcium, abundant liquid intake, increase of urinary excretion by means of the drug furosemide, as well as the administration of glucocorticoids and calcitonin.

If kidney function is adequate, calcium levels can be reliably lowered by infusions of isotonic sodium chloride solution (3–6 liters in 24 hours) with addition of furosemide and, in some circumstances, also 15 mg/kg body weight/hour sodium edetate accompanied by continuous calcium and ECG monitoring. In oligoanuria, in contrast, haemodialysis (calcium-free dialysate) is necessary.

[figure not shown]

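### Stones, nephrocalcinosis and hypercalciuria are contraindicated in the appended product information for two or three of the four arms, but no eligibility criterion names them

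*Protocol*

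**What the plan says.** **Product information.** Appendix 2 (IR calcifediol), section 4.3, contraindicates "Calcium lithiasis" and hypercalciuria. Appendix 3 (cholecalciferol 50,000 IU), section 4.3, contraindicates "Nephrolithiasis and/or nephrocalcinosis" and "Hypercalcaemia and/or hypercalciuria". Appendix 4 (cholecalciferol 800 IU), section 4.3, lists nephrolithiasis, nephrocalcinosis, and any disease or condition that leads to hypercalciuria. Everyone in the paricalcitol arm takes the 800 IU product (Protocol 5.2). Nothing is appended for CTAP101 or for paricalcitol itself.

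**Eligibility.** Protocol 4.2, inclusion 3, requires the subject to "Be without any disease state or physical condition that might impair evaluation of safety and efficacy", or to have no condition that the investigator thinks would interfere with participation. Its listed examples are serum albumin, transaminases and urinary albumin. Protocol 4.3, exclusion 6, starts "Known previous or concomitant serious illness or medical condition, such as malignancy, human immunodeficiency virus" and is qualified by the investigator's opinion. Inclusion 5 and exclusion 2 limit serum calcium and phosphorus, not urinary calcium. The synopsis lists do not name the conditions either.

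**After enrolment.** Section 5.3 adjusts dose on iPTH, corrected serum calcium and phosphorus, and keeps the 800 IU dose fixed. Section 6.8 lets the investigator withdraw a subject for several reasons, including the subject's best interests.

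**The concern.** Eligibility is settled before the arm is known. A site that enrols a patient with known stones, nephrocalcinosis or hypercalciuria cannot steer that patient towards a product without the contraindication. A careful investigator may read inclusion 3 as covering the case, but neither general clause clearly requires exclusion, and sites may decide differently.

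Other contraindications in the same appendices did become criteria: hypersensitivity (exclusion 8), pregnancy (inclusion 8) and raised serum calcium (inclusion 5 and exclusion 2). These did not. Sections 5.1.2 to 5.1.4 point to the appendices for product information and do not say that their contraindications are binding on enrolment.

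The stake is an avoidable exposure. Two arms give the full dose at once on Day 1 and only the Day 29 dose can be held, while the protocol also keeps calcium intake at 1,000 to 1,500 mg a day, with a supplement if needed.

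**Working it through.** The plan states no figure to reproduce. The check sets the contraindication lists beside the eligibility lists and counts arms.

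**Step 1. Contraindications by arm** (section 4.3 of Appendices 2, 3 and 4)

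| Arm | Source | Calcium stones | Non-calcium stones | Nephrocalcinosis | Hypercalciuria |
|---|---|---|---|---|---|
| CTAP101 | none appended | no claim | no claim | no claim | no claim |
| IR calcifediol | Appendix 2 | yes | no | no | yes |
| Cholecalciferol 300,000 IU | Appendix 3 | yes | yes | yes | yes |
| Paricalcitol + cholecalciferol 800 IU | Appendix 4 | yes | yes | yes | diseases or conditions causing it |
| Arms | | 3 | 2 | 2 | 3 |

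On a strict reading of Appendix 4, hypercalciuria with no identified underlying disease is not listed there, so the last count falls to 2. In the fourth arm the contraindication comes from the cholecalciferol component.

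**Step 2. Criteria naming any of these conditions** (Protocol 4.2 and 4.3): 0 of 10 inclusion and 0 of 9 exclusion criteria. The lists show no redaction.

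**Step 3. Chance per known case enrolled.** With 1:1:1:1 allocation each arm has probability 1/4, so the chance is (arms with the contraindication)/4.

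- Calcium stones or a hypercalciuric condition: 3/4 = 75%. The part falling in the two single-dose arms is 2/4 = 50%.
- Non-calcium stones or nephrocalcinosis only: 2/4 = 50%. The part falling in the 300,000 IU arm is 1/4 = 25%.

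These chances do not hold if the weight-based assignment in section 5.4 replaces randomisation.

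**Step 4. Does anything later close the gap?**

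- *Urine collected before dosing.* Section 3.1 has 24-hour collections at Visits 2 and 3. The analytes are redacted. Section 5.4 does not use Visit 2 or 3 laboratory results for eligibility (section 9.3 bars only Visit 3), and no criterion sets a urinary calcium limit.
- *Withdrawal before the first dose.* Section 7.2.1 randomises at the start of Visit 4, with the dose after the t = 0 draw at about 8:00 a.m. The arm is known by then, and section 6.8 can be used at that point. It is permissive, and section 6.8 plans no replacement. A subject withdrawn then stays in the ITT population (SAP 5.1) but, having had no dose, leaves the safety and PK populations (SAP 5.3 and 5.4). In an arm of about 20 that is 1/20 = 5% of the arm.
- *Dose rules.* Section 5.3 has no urinary calcium or stone trigger.

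**The case against.** The strongest objection is that a label contraindication is not this protocol's standard for exclusion. Appendix 3 also contraindicates serious renal impairment, and Appendix 4 says the 800 IU product should not be used in severe renal impairment, yet the trial deliberately enrols down to an eGFR of 15. It also gives 300,000 IU at once where Appendix 3 describes 50,000 IU weekly. This stands: the mismatch is not proof of an oversight or a breach.

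Existing controls also count. Inclusion 3 is mandatory and its first limb does not rest on investigator opinion. The criteria are reviewed again at Visits 2 and 3. Entry requires corrected calcium below 9.8 mg/dL, and serum calcium is checked throughout treatment. These reduce the risk, but none clearly excludes a known stone former with normal serum calcium.

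Some label text is softer. For renal calculi, Appendix 2 section 4.4 allows use "if the benefits outweigh the risks", and Appendix 3 section 4.4 says "There is no clear evidence for causation between Vitamin D3 supplementation and renal stones", while calling the risk plausible. These warnings stand beside the contraindications and do not remove them.

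A reader might infer that a known case, once randomised, is committed to an irreversible Day 1 dose. The documents do not support that: the study is open-label and withdrawal is possible before dosing.

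A reader might also take the urinary calcium instruction in Appendix 4 section 4.4 as a dose rule the trial has omitted. That instruction concerns long-term treatment and is paired with signs of impaired renal function, which every participant has, so it cannot be carried over literally to an 8-week trial. The limit in Appendix 3, "if the calciuria exceeds 300 mg/24 hours in adults", sits in its overdose section.

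**Conclusion.** The point holds as a modest gap in the eligibility criteria. The appended information contraindicates conditions that no criterion names, and the two general clauses do not clearly require exclusion, so a known case may be enrolled and allocated a contraindicated product.

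The 75% and 50% figures are arm counts conditional on such a case being enrolled under 1:1:1:1 randomisation. They do not mean that about 60 or 40 of the 80 participants are at risk. With no prevalence in the documents, no number of cases or harms can be given. Nor are the arms equal hazards: a 300,000 IU single dose and 800 IU daily are counted alike only because both labels list the condition. No claim is made about CTAP101.

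**What to change.** Add to Protocol 4.3 and the synopsis, for all arms, an exclusion for known current nephrolithiasis, nephrocalcinosis or hypercalciuria. Check it against the detailed medical history already taken at Visit 1 (section 6.2), before randomisation at Visit 4. The wording covers current disease because the contraindication lists name the condition and not a past history; resolved stones stay with the investigator under inclusion 3 and exclusion 6. If the sponsor wants to enrol these patients, the protocol should say so and justify it.

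The cost is a protocol amendment with no new procedure. Slightly fewer candidates qualify (number unknown), including some who would have gone to CTAP101, where no contraindication is shown. Unrecognised hypercalciuria would still not be detected.

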5 STUDY TREATMENTS

5.1 Description of Study Medications

Five study medications will be used in the execution of this protocol which are described in sections 5.1.1 through 5.1.5. All study medications will be securely stored for light and heat protection and in accordance to USP Controlled Room Temperature, defined as 20°C to 25°C (68°F to 77°F) with excursions permitted between 15°C to 30°C (59°F to 86°F).

5.1.1 *Description of CTAP101 Capsules*

Dosage form: Soft gel capsule
Dose strength: 30 mcg calcifediol ER capsule
Product description: Blue oval capsules printed single-sided, centered with the logo O in white. Each bottle contains 30 capsules.
Active component: Calcifediol
Non-active components: Paraffin wax, mineral oil, mono- and diglycerides, dehydrated alcohol, lauroyl polyoxylglycerides, butylated hydroxytoluene, hypromellose, modified starch, carageenan, sodium phosphate dibasic, sorbitol and sorbitan solution, FD&C Blue #1, titanium dioxide, medium chain triglycerides (coconut oil) and ink (white, which may contain titanium dioxide, isopropyl alcohol, propylene glycol, hydroxypropylmethyl cellulose 2910)

5.1.2 *Description of Calcifediol IR Capsules*

Dosage form: Soft gel capsule
Dose strength: 266 mcg calcifediol IR capsule
Product description: Orange capsule. Each Al-Al blister or PVC/PVDC-Al blister pack carton contains 10 capsules.
Active component: Calcifediol
Non-active components: Absolute anhydrous ethanol, medium chain triglycerides, gelatin, vegetable glycerin, sorbitol (70%) (E-420), titanium dioxide (E-171), yellow-orange dye S (E-110) and purified water.

For product information, refer to [APPENDIX 2](#).

5.1.3 *Description of High-Dose Cholecalciferol Capsules*

Dosage form: Soft gel capsule
Dose strength: 50,000 IU cholecalciferol capsule
Product description: Red, oval-shaped capsule with “50” printed in white ink. Each PVDC/aluminum foil blister pack with cardboard carton contains 3 capsules.

Active component: Cholecalciferol
Non-active components: All-rac- α -tocopherol (E307), medium chain triglycerides, glycerol, gelatin, Allura Red AC (E129), Opacode® white imprinting ink, shellac (E904), titanium dioxide (E171) and simethicone.

For product information, refer to [APPENDIX 3](#).

5.1.4 Description of Low-Dose Cholecalciferol Capsules

Dosage form: Soft gel capsule
Dose strength: 800 IU cholecalciferol capsule
Product description: Pink, oval-shaped capsule with “0.8” printed in white ink. Each PVDC/aluminum foil blister with cardboard carton contains 28 capsules.
Active component: Cholecalciferol
Non-active components: All-rac- α -tocopherol (E307), medium chain triglycerides, glycerol, gelatin, Allura Red AC (E129), Opacode® white imprinting ink, shellac (E904), titanium dioxide (E171) and simethicone.

For product information, refer to [APPENDIX 4](#).

5.1.5 Description of Paricalcitol Capsules

Dosage form: Soft gel capsule
Dose strength: 1 mcg paricalcitol capsule
Product description: The 1 mcg capsule is an oval, gray, soft gelatin capsule imprinted with Abbott “a” logo and ZA, and is packaged in bottles of 30 (NDC 0074-4317-30), or an equivalent, U.S. approved generic alternate source.
Active component: Paricalcitol
Non-active components: Medium chain triglycerides, alcohol and butylated hydroxytoluene, gelatin, glycerin, titanium dioxide, iron oxide black and water.

5.2 Dosing Plan

Approximately 80 subjects will be randomized 1:1:1:1 (approximately 20 per arm) to receive one of the listed study medications with a sufficient quantity of a non-alcoholic beverage to enable swallowing of the capsules:

- 1) CTAP101 Capsules 60 mcg once daily outside of the phase 1 unit at bedtime, except on Days 1 and 29 when dosing will occur in the phase 1 unit in the morning before breakfast.
- 2) IR calcifediol 266 mcg in the phase 1 unit before breakfast on the mornings of Day 1 and Day 29.
- 3) Cholecalciferol 300,000 IU (high-dose) in the phase 1 unit before breakfast on the mornings of Day 1 and Day 29.

4) Paricalcitol 1 mcg plus cholecalciferol 800 IU (low-dose) once daily outside of the phase 1 unit in the morning before breakfast, except on Days 1 and 29 when dosing will occur in the phase 1 unit before breakfast.

After 4 weeks of treatment, subjects who are receiving paricalcitol will double the dose to 2 mcg plus cholecalciferol 800 IU once daily in the morning before breakfast provided that (a) the plasma iPTH has not decreased by at least 30% from pretreatment BL and remains above 70 pg/mL, (b) corrected serum calcium is <9.8 mg/dL, and (c) serum phosphorus is <5.5 mg/dL. Subjects who are receiving CTAP101 Capsules, IR calcifediol or cholecalciferol (300,000 IU) will not undergo upward dose titration.

